#### 13.1.2 Secondary Endpoints

##### Overall Survival (OS)

The secondary endpoint of this study is the overall survival, defined as the time from randomization to death, from any cause. Patients who do not have an OS event will be censored for OS at the date they were last known to be alive.

##### Adverse Events (AEs)

CTCAE AEs and grade for each type of AE will be recorded for each patient separately for the first 12 cycles (mFOLFOX6 +/- atezolizumab) and the 6 months of continuation of atezolizumab. Similarly, scores (0-4) and maximum score for each PRO-CTCAE item will be recorded for each patient ( $\geq 18$  years of age) separately for these two periods.

## 13.2 Sample Size and Accrual

We anticipate randomizing a maximum of 700 adult patients (350 per arm) per statistical design. Patients aged 12 to <18 years old will be accrued and randomized, but they will not be counted toward the sample size of 700. If the study reaches full accrual of 700 adult patients, enrollment will be closed to both adult and patients aged 12 to <18 years at the same time.

When both NSABP C-08 and NCCTG N0147 adjuvant trials were simultaneously accruing patients, the NSABP C-08 trial accrued 110-130 patients/month and NCCTG N0147 concurrently accrued 20-30 patients/month. Of these 150 patients/month accrual capacity, we estimate that 12% of colon cancers will show dMMR which calculates to 18 patients/month or 216 patients/year.

One and a half years after trial opening, if the accrual rate exceeds the projection (e.g. >25 patients /month), we will consider amending the protocol to raise the accrual target and to allow the detection of a hazard ratio (HR) of  $> 0.6$ .

### 13.2.1 Pathology Considerations

We recognize that local/reference lab testing and central lab confirmatory testing may be performed using different antibodies and platforms for immunohistochemistry. Accordingly, and because of concerns over potential discrepant local/reference versus central testing results, central confirmation review will be performed retrospectively for all samples that had local or site-selected reference lab dMMR testing performed. We will examine the concordance rate after the first 100 samples have been tested and continue monitoring the rate every 100 samples thereafter. The discrepancy rate will be closely monitored for all reviewed samples by the A021502 Statisticians. If it is determined that the discrepancy rate of reviewed samples is high enough to impact the study power (e.g. decrease the study power to less than 85%), then an amendment to increase the sample size to account for this increased discrepancy rate may be considered.

## 13.3 Power Justification

The best historical data available on the outcome of patients with stage III colon cancer comes from Intergroup Study N0147, where the 3-year DFS in MSI-H stage III patients treated with mFOLFOX6 was 75% [40]. We assume an accrual period of 3.24 years, minimum follow-up on all patients of 2.05 years, exponential survival, and that a one-sided log-rank test for superiority will be conducted at level 0.025. Additionally, we assume a dropout rate of 1.25% per year. Based on these assumptions, a sample size of 350 adult patients per arm (700 adult patients in total) will result in 165 events which are required to provide 90% power to detect a hazard ratio (HR) of 0.6 between the two treatment arms. The 3-year DFS estimate for the atezolizumab arm corresponding to this HR is 84.147%.

### 13.4 Statistical Analysis Plan

#### 13.4.1 Primary Endpoint

##### Treatment Efficacy Decision Rules

**Interim Analysis:** Two interim analyses will be performed to assess treatment futility and superiority. The first interim analysis, for both efficacy and futility, will be performed at the time at which 50% of the projected number of events have occurred. The second interim analysis is for efficacy only and will be performed at the time at which 75% of the projected number of events have occurred. The number of DFS events will be the total number of DFS events observed from both adult and patients aged <18 years. O'Brien-Fleming type stopping boundary will be used to control for overall alpha level. Gamma family spending function with parameter -5 will be used for futility boundary. The futility boundary will be considered non-binding. The specific hazard ratio and critical p-values for declaring superiority or futility at each analysis are specified in table below. Specifically, for example, at 1st interim analysis, if the hazard ratio of mFOLFOX6+atezo vs. mFOLFOX6 alone is greater or equal to 1.021 (equivalently, p-value  $\geq 0.538$ ), the mFOLFOX6+atezo regimen will be considered inefficacious; if the hazard ratio is less or equal to 0.523 (equivalently, p-value  $\leq 0.002$ ), the mFOLFOX6+atezo regimen will be deemed effective. When DFS crosses either futility or efficacy boundary, the accrual will be suspended (if still ongoing), the enrolled patients followed per protocol, and the data will be reported.

**Final Analysis:** The primary efficacy analysis will be performed at the time where 165 DFS events have occurred. The number of DFS events will be the total number of DFS events observed from both adult and patients aged <18 years. The specific hazard ratio and critical p-values for declaring superiority or futility at each analysis are specified in table below. Specifically, at the final analysis, if the hazard ratio is less or equal to 0.731 (equivalently, p-value  $\leq 0.022$ ), the mFOLFOX6+atezo regimen will be deemed effective; otherwise, mFOLFOX6+atezo regimen will be considered to have not met the criteria for efficacy.

Analysis time point (% events)	Number of events	Critical p-value for efficacy	HR for efficacy	Critical p-value for futility	HR for futility
50%	83	0.002	0.523	0.538	1.021
75%	124	0.009	0.655	NA	NA
100%	165	0.022	0.731	0.022	0.731

**Operating Characteristics:** The table below shows the operating characteristics assuming the DFS follows exponential survival functions. The table below includes the operating characteristics according to the monitoring plan outlined above. The proportion of times that 1) the study would stop early at 1st interim analysis due to futility of mFOLFOX6+atezo, 2) the study would stop early at 1st or 2nd interim analyses due to efficacy of mFOLFOX6+atezo, and 3) the study would conclude mFOLFOX6+atezo is superior to mFOLFOX6 alone at the final analysis, are tabulated by true 3-year rates and equivalent true hazard ratio for DFS by treatment groups.

True 3-year DFS rate†		True Hazard Ratio	%‡ of times the study will be stopped early for futility		%‡ of times the study will be stopped early for efficacy		%‡ of times that mFOLFOX6 + atezo is superior at the final analysis
mFOLFOX6 alone	mFOLFOX6 + atezo		1 st interim analysis	2 nd interim analysis	1 st interim analysis	2 nd interim analysis	
0.75	0.841	0.60	0.81	NA	24.96	42.59	89.26
0.75	0.829	0.65	2.07	NA	15.50	35.93	77.51
0.75	0.818	0.70	4.69	NA	13.49	27.14	59.37
0.75	0.794	0.8	13.17	NA	2.52	11.35	29.74
0.75	0.772	0.9	28.16	NA	0.6	3.51	5.84
0.75	0.75	1	46.12	NA	0.13	0.8	2.66

DFS: disease-free survival

† Although we use the 3-year rates to illustrate each scenario, the hypothesis testing is based on the entire survival curve.

‡ Proportions are based on 10,000 replicates in the simulation study.

**Analysis Plan:** DFS will be compared between treatment arms using the stratified log rank test at one-sided level 0.025. The stratification factors listed in [Section 4.6](#), as collected at the time of randomization in OPEN, will be used for the analysis. If there are zero DFS events observed in any of the strata, unstratified log-rank test will be used. If zero DFS events are observed in a certain stratum at an interim analysis and unstratified log-rank is used, all subsequent analyses for DFS will use unstratified log-rank test. The HR for DFS will be estimated using a Cox proportional hazards model and the 95% CI for the HR will be provided. If a stratified log-rank test is used, stratified HR will be considered, and if an unstratified log-rank test is used, unstratified HR will be considered. Kaplan-Meier methodology will be used to estimate the median DFS for each treatment arm, and Kaplan-Meier curves will be produced. Brookmeyer-Crowley methodology will be used to construct the 95% CI for the median DFS for each treatment arm (Brookmeyer and Crowley 1982).

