#### 4.6 Stratification Factors and Treatment Assignments

##### Permuted Block

After a patient is registered, they will be assigned to one of the two treatment arms (Arm 1 vs. Arm 2) in a **1:1** ratio utilizing a permuted block schedule [39]. The stratification factors for this study are as follows:

- Number of Positive Lymph Nodes: N1 (1-3 positive nodes)/N1C vs. N2 ( $\geq 4$  positive nodes) (per AJCC 7)
- T Stage: Tx/T1-T3 vs. T4
- Primary Tumor Location: proximal (cecum, ascending colon, hepatic flexure, and transverse colon) vs. distal (splenic flexure, descending colon, sigmoid colon, and rectosigmoid junction)

When combined, these stratification factors create eight stratum levels, each of which having its own patient allocation schedule. The possible block size for this study is four.

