### **13.4.2 Secondary Endpoints**

**Overall Survival:** The distribution of overall survival will be estimated using the method of Kaplan-Meier. Overall survival will be compared between treatment arms using the stratified log-rank test, only if DFS is statistically significant. The stratification factors listed in [Section 4.6](#), as collected at the time of randomization in OPEN, will be used

for the analysis. If there are zero OS events observed in any of the strata, unstratified log-rank test will be used. If zero OS events are observed in a certain stratum at an interim analysis and unstratified log-rank is used, all subsequent analyses for OS will use unstratified log-rank test. The HR for OS will be estimated using a Cox proportional hazards model and the 95% CI for the HR will be provided. If a stratified log-rank test is used, stratified HR will be considered, and if an unstratified log-rank test is used, unstratified HR will be considered.

We assume an accrual period of 3.24 years, with accrual target of 700 patients, exponential survival, and that a one-sided log-rank test for superiority will be conducted at level 0.025. Five-year OS in MSI-H stage III patients treated with mFOLFOX6 was 78.3% (unpublished manuscript by Sinicrope et al.). Based on these assumptions, 163 events are required to provide 90% power to detect a hazard ratio (HR) of 0.6 between the two treatment arms. The 5-year OS estimate corresponding to this HR is 86.35%.

There will be one interim analysis for overall survival (OS) which will be carried out if DFS crosses an interim efficacy stopping boundary, or at the time of the final DFS analysis, if no interim DFS boundary is crossed. The interim analysis will be for efficacy only. One final OS analysis will be conducted after approximately 163 deaths are observed. The number of OS events will be the total number of OS events observed from both adult and patients aged <18 years. The O'Brien-Fleming type stopping boundary will be used to control for overall alpha level. The HR and critical p-values for declaring efficacy for OS are specified in the table below.

Analysis Time Point (% death events)	Expected Number of OS Events	Critical P-Value for Efficacy (1-sided)	HR for Efficacy
1 st DFS IA (28%) a	46	0.00002	0.302
2 nd DFS IA (42%) a	68	0.001	0.451
DFS PA (57%) b	93	0.003	0.563
100% (Final)	163	0.024	0.734

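### A single stratum with no events switches the DFS and OS tests and hazard ratios to unstratified for all later looks; the switch is unnecessary, though its average cost in DFS power is small

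*Combined protocol and SAP*

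**What the plan says.** - **Strata.** Section 4.6 stratifies randomisation by nodal stage (N1/N1C against N2), T stage (Tx/T1-T3 against T4) and tumour location (proximal against distal): "these stratification factors create eight stratum levels, each of which having its own patient allocation schedule". Blocks are of four.
- **Primary test.** Section 13.4.1, Analysis Plan: "DFS will be compared between treatment arms using the stratified log rank test at one-sided level 0.025", using the Section 4.6 factors as recorded at randomisation.
- **Switch and lock-in.** The same paragraph continues: "If there are zero DFS events observed in any of the strata, unstratified log-rank test will be used". If that happens at an interim look, "all subsequent analyses for DFS will use unstratified log-rank test".
- **Estimate.** The hazard ratio follows the test: "if an unstratified log-rank test is used, unstratified HR will be considered".
- **OS.** Section 13.4.2 has the same trigger, "If there are zero OS events observed in any of the strata, unstratified log-rank test will be used", and the same lock-in, "all subsequent analyses for OS will use unstratified log-rank test".
- **What is absent.** No reason is given for the fallback. The two sensitivity analyses in Section 13.4.1 concern missed disease assessments only, so no stratified result is planned once the switch has occurred.

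**The concern.** A stratum without events does no harm to a stratified log-rank test or a stratified Cox model. The plan nevertheless gives up all stratification when any one of eight cells has no event, and keeps it given up after that cell has filled. If the factors are prognostic, the unstratified test is less efficient and its hazard ratio usually lies nearer to 1 than the within-stratum one. Section 1.3 describes N2 as prognostically poor and MSI tumours as mostly right-sided, so some distal cells are probably small. What is at stake is some efficiency, and a primary test and reported hazard ratio whose form is settled by chance sparseness at an early look.

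**Working it through.** **1. The plan's own figure.** With a hazard ratio of 0.6, one-sided 0.025 and 90% power, Schoenfeld's formula gives 4 × (1.960 + 1.282)² / (ln 0.6)² = 161.1, or 162 events; Freedman's gives 169. The plan's 165 (Section 13.3) lies between them. O'Brien-Fleming-type bounds at 83, 124 and 165 events give hazard ratios of 0.523, 0.655 and 0.731, as in the Section 13.4.1 table, and group-sequential power of 90.2%. The design is reproduced.

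**2. Contribution of an event-free stratum.** The stratified statistic is Z = Σ(O − E) / √ΣV, summed over strata. O, E and V within a stratum are sums over its event times. With no event times, O − E = 0 and V = 0 (also confirmed numerically), and the stratum adds no term to the stratified Cox partial likelihood. The test stays computable and unchanged.

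**3. Chance of triggering.** Stratum shares and factor effects are not in the documents, so what follows rests on assumptions. With q the share of events falling in a stratum and D the number of events, P(at least one event-free stratum) ≈ 1 − Π(1 − e^(−qD)). Take shares N2 35%, T4 25%, distal 15%, with N2 and T4 each doubling the hazard. At D = 83 the four distal cells expect 3.60, 2.40, 3.87 and 2.58 events, so their chances of having none are 0.027, 0.091, 0.021 and 0.076. The proximal cells are negligible. Then 1 − 0.973 × 0.909 × 0.979 × 0.924 = 0.20, in agreement with the simulated 20.2% below.

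**4. Simulation of the rule.** Inputs: 700 patients, eight strata, permuted blocks of four, 3.24 years of accrual, dropout 1.25% a year, control 3-year DFS 75%, within-stratum hazard ratio 0.6, looks at 83/124/165 events, 20,000 replicates per row.

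| Assumed factor effect | Shares N2/T4/distal | Patients in smallest stratum | Trigger at 83/124/165 events | Power: always stratified / plan's rule / always unstratified |
|---|---|---|---|---|
| None | 35/25/15% | 9 | 44.6 / 24.4 / 13.3% | 89.5 / 89.6 / 89.7% |
| N2, T4 HR 1.5 | 40/30/25% | 21 | 3.6 / 0.5 / 0.1% | 89.0 / 89.0 / 88.8% |
| N2, T4 HR 2.0 | 35/25/15% | 9 | 20.2 / 6.2 / 2.1% | 89.2 / 89.1 / 88.3% |
| N2, T4 HR 2.5, distal 1.2 | 35/25/10% | 6 | 33.2 / 12.5 / 4.8% | 89.8 / 89.2 / 87.7% |
| N2, T4 HR 3.0 | 40/30/15% | 13 | 22.5 / 6.4 / 1.6% | 89.7 / 88.8 / 85.8% |

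A cell that is empty at a later look was also empty at the first, so the 83-event figure is the overall trigger probability. By 165 events it is at most about 13%, so most switches would come from the lock-in.

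A second set of assumptions, with N2 and T4 at HR 2, gives triggers at 83 events of 3% (shares 45/30/25%), 14% (40/20/20%) and 39% (35/15/15%). The full-switch losses there are 89.9 − 87.9 = 2.0, 88.8 − 88.0 = 0.8 and 88.5 − 87.1 = 1.4 points. Trigger times loss is about 0.06, 0.1 and 0.5 points.

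**5. Other effects.** At a hazard ratio of 0.7 with the strongest factors (4,000 replicates), power is 61.5% always stratified, 59.9% under the rule and 53.9% always unstratified. Under the null, rejection is about 2.3-2.8% stratified and 1.8-2.7% unstratified, so there is no inflation.

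**6. OS.** Over the assumed ranges, the trigger probability is 22-76% at 46 deaths, 8-56% at 68, 2-37% at 93 and 0.2-12% at 163. There is only one OS interim, and its timing follows DFS. By the plan's operating characteristics at a hazard ratio of 0.60, DFS stops for efficacy at the first interim in 24.96% of trials and at the second in 42.59%. Together that is 67.55% in which the OS interim would fall at about 46 or 68 deaths. These are trigger probabilities only; no OS power loss is claimed.

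**The case against.** **The rule is conditional.** Comparing a stratified with an unstratified trial overstates the cost, because the switch happens only if triggered. This stands, and the average under the rule itself is the figure to use.

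**Planned power does not depend on stratification.** Section 13.3 powers a log-rank test from pooled 3-year rates, without mention of strata. If 0.6 is read as a marginal hazard ratio, the unstratified test keeps roughly the planned 90% and stratification is a gain forgone. The difference between the two hazard ratios is then one of marginal and conditional effects, not an error of estimation. This also stands. It bears on how the loss is described, but gives no reason to discard the strata because one cell has no event.

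**The rule is pre-specified.** The trigger is a pooled count per stratum that ignores treatment arm, leaves no discretion, and keeps one form of test afterwards. A reader might infer an inflated type I error or an invalid primary analysis; neither the text nor the simulation supports that. The stratified test at every look gives the same consistency without the switch.

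**Prognostic strength is not established for dMMR disease.** Section 1.3 gives no hazard ratio for N2. Section 1.2 takes the T4/N2 risk grouping from a pooled analysis that did not examine dMMR status, and says that its relevance to dMMR tumours is unknown. Hence the ranges, which include no effect at all.

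**Conclusion.** The switch is unnecessary and should go. Under the assumed stratum shares and factor effects, it has about a 3% to 45% chance of being triggered at the 83-event DFS look. It costs on average about 0 to 1 point of DFS power at a hazard ratio of 0.6. If the trial is fully switched the loss is 0 to about 4 points, and it is nil within simulation error when the factors are weak or not prognostic. The algebra in step 2 is certain; the sizes rest on inputs that the documents do not give.

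A reader might conclude that the trial is underpowered or that the 165-event target is wrong. Neither follows: the event target is reproduced and the average loss is small. The remaining fault is avoidable inefficiency, and a final test and reported hazard ratio that a sparse cell at an early look can decide.

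**What to change.** In Sections 13.4.1 and 13.4.2, delete the zero-event switch and its lock-in. Use the stratified log-rank test and the stratified Cox hazard ratio on the Section 4.6 factors at every DFS and OS look. Report the unstratified test and hazard ratio as a sensitivity analysis.

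Make the change without reference to unblinded results. If a look has already triggered the switch, add the stratified analysis as a documented sensitivity analysis.

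Pooling strata over tumour location is not needed, and nothing in the documents shows location to be the least prognostic of the three factors.

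The cost is a few sentences in two sections. It needs no extra patients, events or data, and the stopping boundaries are unchanged.

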#### **Sensitivity Analysis Plan:**

- 1) One additional censoring rule will be added for missed disease assessments. For patients with a DFS event who missed one or more scheduled assessments immediately prior to the DFS event, the DFS event will be censored at the last tumor assessment prior to the missed disease assessment.
- 2) For patients with a DFS event who missed one or more scheduled disease assessments immediately prior to the DFS event, the DFS event will be dated on the earliest missed assessment (after the last known tumor assessment). This sensitivity analysis is aimed to assess the impact of missing disease assessment.

### **13.4.2 Secondary Endpoints**

**Overall Survival:** The distribution of overall survival will be estimated using the method of Kaplan-Meier. Overall survival will be compared between treatment arms using the stratified log-rank test, only if DFS is statistically significant. The stratification factors listed in [Section 4.6](#), as collected at the time of randomization in OPEN, will be used

for the analysis. If there are zero OS events observed in any of the strata, unstratified log-rank test will be used. If zero OS events are observed in a certain stratum at an interim analysis and unstratified log-rank is used, all subsequent analyses for OS will use unstratified log-rank test. The HR for OS will be estimated using a Cox proportional hazards model and the 95% CI for the HR will be provided. If a stratified log-rank test is used, stratified HR will be considered, and if an unstratified log-rank test is used, unstratified HR will be considered.

We assume an accrual period of 3.24 years, with accrual target of 700 patients, exponential survival, and that a one-sided log-rank test for superiority will be conducted at level 0.025. Five-year OS in MSI-H stage III patients treated with mFOLFOX6 was 78.3% (unpublished manuscript by Sinicrope et al.). Based on these assumptions, 163 events are required to provide 90% power to detect a hazard ratio (HR) of 0.6 between the two treatment arms. The 5-year OS estimate corresponding to this HR is 86.35%.

There will be one interim analysis for overall survival (OS) which will be carried out if DFS crosses an interim efficacy stopping boundary, or at the time of the final DFS analysis, if no interim DFS boundary is crossed. The interim analysis will be for efficacy only. One final OS analysis will be conducted after approximately 163 deaths are observed. The number of OS events will be the total number of OS events observed from both adult and patients aged <18 years. The O'Brien-Fleming type stopping boundary will be used to control for overall alpha level. The HR and critical p-values for declaring efficacy for OS are specified in the table below.

Analysis Time Point (% death events)	Expected Number of OS Events	Critical P-Value for Efficacy (1-sided)	HR for Efficacy
1 st DFS IA (28%) a	46	0.00002	0.302
2 nd DFS IA (42%) a	68	0.001	0.451
DFS PA (57%) b	93	0.003	0.563
100% (Final)	163	0.024	0.734

a. If DFS crosses efficacy stopping boundary at that analysis

b. If DFS was not crossed at either DFS interim analysis

IA = interim analysis; PA = primary analysis

The actual critical values used will be determined by the observed OS events at the time of the DFS analysis as well as that (those) at the previous DFS analysis (analyses) where applicable.

